**Specific Aim 3:** To evaluate effects of DF I-PRO therapy on overall health status reflected by the number of pneumonia diagnoses and overall hospital readmission rates in post-stroke subjects undergoing DF I-PRO therapy compared to controls.

**Hypothesis 3a:** There will be a greater decrease from pre- to post-enrollment in the number of pneumonia diagnoses and overall hospital readmissions for those subjects who complete 12 weeks of DF I-PRO therapy compared to controls.

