For those patients who have already had a recent videofluoroscopic swallow study, the consent process will take place after completion of this swallow study. Potential subjects must meet diagnostic criteria for dysphagia on their videofluoroscopic swallowing examination. If during this exam the patient meets specified inclusion criteria, the UW ENT clinicians will subsequently approach the patient regarding participation. If the patient is interested in participating, the study staff will be notified and will follow-up with the patient. Once general eligibility for meeting inclusion criteria is confirmed by review of the patient's medical record, the general purpose of

the study and the length of the study will be explained to potential participants either by phone (if outpatient) or in-person if an inpatient or at hospital for outpatient visit. If the potential participant expresses interest, more details about the study will be provided, including a copy of the consent form. Then, the same process for obtaining consent will be followed.

**Inclusion criteria:** 1) clinical diagnosis of unilateral or bilateral ischemic or hemorrhagic strokes by attending physician (according to the National Institute of Health Stroke Scale (NIHSS)); 2) within 6 months of acute stroke diagnosis; 3) referral for a videofluoroscopic swallowing study; 4) a score of 3 or higher on the Penetration-Aspiration scale OR a score of 2 on the Residue scale at any location (oral cavity, valleculae, or pharynx) that is instrumentally documented by a participating SLP during the standardized videofluoroscopic swallowing study; 4) between the ages of 21 and 95; 5) ability to perform the strengthening protocol independently or with the assistance of a caregiver; 6) physician approval of medical stability to participate and 7) decision-making capacity to provide informed consent (confirmed through discussion with the subject's primary physician); 8) phone access; and 9) ability to return to the clinic for required follow-up appointments.

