## **Outcomes**

The *primary outcome measure* will be changes in the *one repetition maximum (IRM) isometric lingual pressures* measured at the front and back sensors of the device. Secondary outcomes include *bolus flow durational measurements* taken from videofluoroscopic recordings, *swallowing pressures, SWAL-QOL scores, and FOIS scores*. In addition, we will compare the *number of pneumonia diagnoses* for community, hospital-acquired, and aspiration pneumonia for the same period of time prior to enrollment and following completion of the study (up to nine months). We also will track the *number of hospital re-admissions* for the same period of time prior to enrollment and following completion (up to 9 months). Treatment compliance also will be tracked within the SwallowStrong® device and will serve as a covariate in statistical analyses.

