*Saliva Analyses:* Each measure of viscoelasticity and lubrication properties will be recorded three times per sample. Apparent viscosity will be determined using a TA Discovery, HR-2 rheometer (TA Instruments, New Castle, DE, USA) equipped with a Peltier plate temperature control unit (233212.902). All measurements will be carried out with a flat plate geometry with a diameter of 20 mm and an operating gap of 200 µm. Each sample will first be allowed to equilibrate for 30 seconds at 37°C on the rheometer stage. Viscosity will then be measured at 37°C at shear rates ranging from 0.1 to 100 1/s. In [name] laboratory, samples will be frozen until all have been collected. Then, an enzyme-linked immunosorbent assay (ELISA) will be completed in order to quantify levels of the protein Substance P within the samples.

**Hospital Readmissions and Pneumonia Diagnoses:** The number of pneumonia diagnoses and overall hospital readmissions will be compared for the same period of time prior to enrollment and following completion of the study (up to 9 months) for each subject. Discharge reports will be used to tally the number of readmissions and clinic notes will be reviewed to determine number of pneumonia diagnoses (community, hospital-acquired, and aspiration pneumonia) for each subject.

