## **Statistical Analyses**

Prior to data analyses, the data collected under this study will be combined with data from its VA counterpart (IRB #2014-0939). Statistical analyses will be performed using this combined data set.

**Aim 1:** A repeated measures analysis model will be used to model changes in tongue strength in treatment and control groups, adjusted for age, gender, and baseline tongue strength. Each subject will have three observations: change between baseline and 8 weeks, baseline and 12

weeks, and 8 weeks and 12 weeks. This model will allow for comparison of differences between a) treatment durations (dose response) and b) between control and treatment groups.

**Aim 2:** Changes in oral intake and swallowing quality of life between baseline and 8 weeks, baseline and 12 weeks, and 8 weeks and 12 weeks will be modelled in a repeated measures analysis on treatment, adjusting for age, gender, and baseline outcome.

**Aim 3:** Change in number of new pneumonia diagnoses and number of hospital readmissions over a 1 year period, pre and post-study, will be modelled in linear regression models on treatment, adjusting for age, gender, and pre-study outcome.

All analyses will be performed on a randomized, or intention to treat basis, regardless of the actual treatment received. Study dropout by the subject will result in inclusion of incomplete data for that patient.

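### Aim 3: the pre-to-post decrease can look back across the stroke and is only descriptive; the completer restriction and the post window's start threaten the between-arm contrast

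*Combined protocol and SAP*

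**What the plan says.** - **Hypothesis (Specific Aims, Hypothesis 3a).** "There will be a greater decrease from pre- to post-enrollment in the number of pneumonia diagnoses and overall hospital readmissions", and this is predicted "for those subjects who complete 12 weeks of DF I-PRO therapy compared to controls".
- **Eligibility (Subjects, inclusion criteria).** Subjects enter "within 6 months of acute stroke diagnosis". The recruitment text allows both inpatients and outpatients and gives no proportions.
- **Window (Data Reduction and Analysis).** Counts "will be compared for the same period of time prior to enrollment and following completion of the study (up to 9 months) for each subject". The Outcomes section gives the same rule.
- **Window (Statistical Analyses, Aim 3).** Here the change is taken "over a 1 year period, pre and post-study". It is regressed linearly on treatment, with age, gender and the pre-study count as covariates.
- **Record review (Data Safety and Monitoring, confidentiality paragraph).** Records are read at the one-year point, over equal numbers of months before and after enrolment. The forward window is thus counted from enrolment here, not from completion.
- **Early exit (Intervention).** A subject in either group who no longer meets the dysphagia criteria at the 8-week examination leaves the study.
- **Analysis set (Statistical Analyses).** "All analyses will be performed on a randomized, or intention to treat basis".

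No section limits the look-back to time after the stroke or says how the index stroke admission is treated.

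**The concern.** The look-back is matched in length to the follow-up, not anchored to the stroke. It can therefore reach back before the event that caused the dysphagia, and by a different amount for each subject. A decrease or increase within an arm then compares a mixture of pre-stroke and acute-stroke months with later months. Reporting it as a change in health status, as the earlier clinical program's pre/post percentages were reported, would mislead.

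Two further features bear on the comparison between arms, where randomisation should protect the result. The hypothesis selects treated subjects on something that happens after randomisation and leaves controls unselected. The forward window starts at a point that can depend on the week-8 result, and it leaves out the treatment period itself.

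**Working it through.** The plan gives no figure for Aim 3. Its only power figures (Table 2) concern tongue pressure. A two-sided two-sample t-test with 15 per group, SD 100 hPa and alpha 0.05 gives 75.3%, 56.2%, 35.5% and 18.5%, against the stated 75%, 56%, 35% and 18%. That table is sound and does not bear on this point.

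**1. Pre-stroke share of the look-back.** Let W be the look-back in months and t the months from stroke to enrolment (0 to 6, from the inclusion criteria). Share = max(0, W − t)/W.

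| W | t = 0.25 | t = 3 | t = 6 | Mean, t uniform on 0–6 (assumption) |
|---|---|---|---|---|
| 3 | 92% | 0% | 0% | 25% |
| 6 | 96% | 50% | 0% | 50% |
| 9 | 97% | 67% | 33% | 67% |
| 12 | 98% | 75% | 50% | 75% |

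The least pre-stroke time in a full window is 9 − 6 = 3 months, or 12 − 6 = 6 months. At W = 9 the share falls below half once t exceeds 4.5 months.

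**2. Windows that the timeline allows.** The Study Timeline gives 9 months of enrolment in a 12-month project. Twelve weeks is 84/30.44 = 2.76 months. Counting from completion to a record review at month 12:
- enrolled at month 0: 12 − 2.76 = 9.24 months, capped at 9;
- enrolled at month 9: 12 − 9 − 2.76 = 0.24 months.

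No 12-week subject reaches a 1-year post-study window by then. With enrolment uniform over months 0–9 and t uniform over 0–6 (both assumed), the mean pre-stroke share is 38%, and 31% of subjects have no pre-stroke time in the look-back. If the window runs from enrolment instead (3 to 9 months), the mean share is 55%.

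**3. Change within an arm when therapy does nothing.** Assumed monthly event rates: 0.01 before stroke, 0.15 in the first month after it, 0.04 later; t uniform on 0–6.
- Mean post-stroke events before enrolment: 0.15 × 0.917 + 0.04 × 2.083 = 0.221. Here 0.917 and 2.083 are the mean months spent in month 1 and beyond it.
- W = 9: pre = 0.01 × (9 − 3) + 0.221 = 0.281; post = 0.04 × 9 = 0.360; change = +0.08.
- W = 12: pre = 0.01 × (12 − 3) + 0.221 = 0.311; post = 0.04 × 12 = 0.480; change = +0.17.

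Under these rates the untreated change is an increase. If the index stroke admission were counted as a pre event, the 9-month change for admissions would become 0.08 − 1 = −0.92. A definition that the plan does not give would reverse the sign.

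**4. The between-arm coefficient.** With x the pre-count, y the post-count and g the arm, y − x = a + b·g + c·x is the same model as y = a + b·g + (c + 1)·x. The coefficient b is identical, and time since stroke is balanced in expectation. A simulation under the step 3 rates (15 per arm, 20,000 runs, age and gender omitted) gives:

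| W | Mean b, no effect (Monte Carlo SE) | Rejections at nominal 5% | Mean b, rate ratio 0.5 |
|---|---|---|---|
| 9 | −0.002 (0.002) | 4.3% | −0.17 |
| 12 | +0.003 (0.002) | 4.6% | −0.23 |

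This compares complete randomised arms over fixed windows, so it does not cover steps 5 and 6.

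**5. The completer restriction.** Under the Intervention section, only subjects still dysphagic at week 8 go on to week 12. Treated subjects who complete 12 weeks therefore exclude everyone whose dysphagia resolved by week 8, while the control side as worded still includes such subjects. Each exclusion removes 1/15 = 6.7% of the planned treated group. The direction of bias is not fixed: dropping resolved cases could count against therapy, and dropping those who stopped for other reasons could favour it.

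**6. Start of the post window.** Taking completion to mean each subject's own last study point, it falls at week 8 (56/30.44 = 1.84 months) or week 12 (2.76 months), depending on the week-8 examination. Events in those months fall in neither window. With a 9-month post window, the uncounted share of time since enrolment is 1.84/10.84 = 17% or 2.76/11.76 = 23%. Where the record-review date sets the length, leaving at week 8 adds 2.76 − 1.84 = 0.92 months of follow-up, and an equal look-back.

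**The case against.** The strongest reply is that Hypothesis 3a compares arms, the arms are randomised, and the Aim 3 model estimates a treatment coefficient. Whatever the look-back contains is shared by both arms. This stands, and step 4 bears it out. A reader might infer that Aim 3 would measure time since stroke and not therapy, or could not show a health effect. The documents do not support that: the plan specifies no within-arm test, and the coefficient is unaffected by modelling change instead of the post-count.

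A reader might also infer that the look-back is largely pre-stroke. That holds on average only for the longest windows. The plan says up to 9 months, and its own timeline makes most windows shorter. Nor does counting the index admission guarantee a decrease: one later admission offsets it, and the plan speaks of readmissions without saying that the index stay counts.

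On completers, it can fairly be said that the intention-to-treat sentence covers all analyses, that the week-8 exit applies to both groups, and that these outcomes come from records, so nobody need be lost. If that sentence governs, no subject is dropped. But the hypothesis still names a different and one-sided comparison, and the text does not say which prevails. The intention-to-treat sentence also does not settle when the post window starts.

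**Conclusion.** The point holds in a limited form. A full look-back crosses the stroke by at least 3 months (9-month window) or 6 months (1-year window), with less or none for shorter windows. Each arm's own pre/post change should therefore be descriptive only. The randomised coefficient is not biased by this, although with about 15 per arm chance imbalance in time since stroke remains and the model does not adjust for it.

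The between-arm contrast is threatened by the completer wording, which contradicts intention to treat, and by a post window that omits 8 or 12 weeks of treatment and can start according to the week-8 result. The size of either bias cannot be calculated, because the documents give neither the proportion expected to resolve by week 8 nor any event rates. The mean shares assume uniform enrolment and time since stroke, and the within-arm changes rest on illustrative rates; the 3- and 6-month minimums need neither. Severity is modest: this is the third aim of a pilot, and these outcomes are listed after the primary and secondary ones.

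**What to change.** - Restate Hypothesis 3a as a between-arm comparison of pneumonia diagnoses and readmissions counted from randomisation in all randomised subjects. Delete the restriction to those completing 12 weeks.
- Say expressly that the end-of-study record review includes subjects who left at week 8.
- Allow for each subject's follow-up time, for example with a count model and a person-time offset, in place of linear regression of the change.
- Add time from stroke to enrolment as a covariate.
- State that the index stroke admission is not a readmission, including for subjects randomised before discharge.
- Keep any pre/post change as a description only.
- Reconcile the two window lengths (up to 9 months; 1 year) and the two starting points (completion; enrolment).

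The cost is wording in five places: Specific Aims, Outcomes, Data Reduction and Analysis, the confidentiality paragraph and Statistical Analyses. No new procedure is needed, since records are already reviewed and the stroke date is needed for eligibility. The downside is that the result becomes less directly comparable with the earlier clinical program's pre/post percentages.

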## **Research Design and Methods:**

### **Subjects**

Forty medically stable unilateral ischemic stroke subjects with dysphagia will be consecutively accrued from the University of Wisconsin Hospital and Clinics (UWHC). There is a counterpart application that is currently under review with the IRB for enrollment of Veterans into this study as well (IRB #2014-0939). Therefore, the forty subjects will be the sum of those enrolled through this protocol as well as the VA protocol under review.

Recruitment Process: Inpatients or Outpatients who meet the inclusion criteria related to their stroke diagnosis (unilateral or bilateral ischemic or hemorrhagic stroke within 6 months of diagnosis) with none of the exclusion criteria will be referred by [name], a stroke neurologist and Medical Director of the UW Comprehensive Stroke Program or a member of his team, to participate in the study. Patients also may be referred by the UW Voice and Swallowing Clinic clinicians involved in this study. In order to have earlier identification of inpatients who are potential participants, [name], an Emergency Department physician, will be screening the list of admitted emergency patients daily for those who meet study criteria based on stroke diagnosis. He will then notify [name] of these potential participants and she will confirm eligibility with [name], his team, or the ENT clinicians. Once general eligibility for meeting inclusion criteria is confirmed via [name] review of the patient's medical record and it has been determined that the patient will require videofluoroscopic examination (VFSE) of his/her swallowing as part of routine clinical care, [name], a member of his team, or a clinician from the UW Voice and Swallowing Clinic will ask the patient to fill out a permission-to-contact form and subsequently will notify [name] that this form has been signed so that she can follow-up with the patient.

If an Outpatient, those who meet inclusion criteria and require a VFSE will be contacted by phone by [name] or their SLP clinician to inquire regarding interest in the study. If they indicate interest and verbally provide permission to be contacted, [name] or [name] would be notified and will follow-up with the patient. The general purpose and the length of the study will be explained to potential participants either by phone (if outpatient) or in-person if an inpatient or at the hospital for outpatient visit. [name] will see inpatients in their hospital room to obtain informed consent prior to the VFSE. For Outpatients, a 30 minute visit in the Voice and Swallowing Clinic or Speech, Swallowing, and Dining Enhancement (SWAL-ADE) Program's laboratory immediately prior to their VFSE will be scheduled during which time more information about the study will be provided and informed consent will take place by [name]. Throughout the informed consent process, the potential participant will be provided with multiple opportunities to seek clarification of any information that is presented. Following review of the informed consent document, the potential participant will be asked to accept or decline further participation. Should s/he accept, the participant will indicate agreement with all study procedures by signing the informed consent form. The participant will be provided with a copy of the consent form, along with contact information for affiliated investigators.

Following consent, the subject will undergo a videofluoroscopic examination of swallowing according to the protocol outlined below. If the subject does not meet diagnostic criteria for dysphagia on the videofluoroscopic swallowing exam (Penetration-Aspiration Scale score of 3 or higher and/or a score of 2 on the Residue scale at any location), s/he will not be randomized to a study group and will no longer continue participation in the study.

For those patients who have already had a recent videofluoroscopic swallow study, the consent process will take place after completion of this swallow study. Potential subjects must meet diagnostic criteria for dysphagia on their videofluoroscopic swallowing examination. If during this exam the patient meets specified inclusion criteria, the UW ENT clinicians will subsequently approach the patient regarding participation. If the patient is interested in participating, the study staff will be notified and will follow-up with the patient. Once general eligibility for meeting inclusion criteria is confirmed by review of the patient's medical record, the general purpose of

the study and the length of the study will be explained to potential participants either by phone (if outpatient) or in-person if an inpatient or at hospital for outpatient visit. If the potential participant expresses interest, more details about the study will be provided, including a copy of the consent form. Then, the same process for obtaining consent will be followed.

**Inclusion criteria:** 1) clinical diagnosis of unilateral or bilateral ischemic or hemorrhagic strokes by attending physician (according to the National Institute of Health Stroke Scale (NIHSS)); 2) within 6 months of acute stroke diagnosis; 3) referral for a videofluoroscopic swallowing study; 4) a score of 3 or higher on the Penetration-Aspiration scale OR a score of 2 on the Residue scale at any location (oral cavity, valleculae, or pharynx) that is instrumentally documented by a participating SLP during the standardized videofluoroscopic swallowing study; 4) between the ages of 21 and 95; 5) ability to perform the strengthening protocol independently or with the assistance of a caregiver; 6) physician approval of medical stability to participate and 7) decision-making capacity to provide informed consent (confirmed through discussion with the subject's primary physician); 8) phone access; and 9) ability to return to the clinic for required follow-up appointments.

**Exclusion Criteria:** 1) degenerative neuromuscular disease; 2) prior surgery to the head and neck region that would affect muscles involved in swallowing; 3) history of radiotherapy or chemotherapy to the head and neck; 4) patient unable to complete the exercise program; 5) taking medications that depress the central nervous system; 6) allergy to barium (used in videofluoroscopic swallowing assessment); 7) currently pregnant.

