## **Intervention**

Participants who meet criteria for dysphagia on the videofluoroscopic swallowing examination will be randomly assigned into one of two groups: 1) a control group that will be receiving compensatory treatments only or 2) 12-week DF I-PRO therapy *plus* compensatory treatments, such as thickened liquids and/or postural strategies during natural swallowing activities for 12 weeks. Patients will be enrolled and trained in DF I-PRO therapy by [name] who regularly uses the SwallowSTRONG®-facilitated I-PRO therapy in clinical practice or a UW Voice and Swallowing clinician involved in this study who has been adequately trained in DF I-PRO therapy. Regardless of the treatment group to which a subject is randomized, they will be evaluated in the hospital at baseline and 8-week time points. If a patient in either group no longer meets criteria for dysphagia (Penetration-Aspiration Scale score of 3 or higher OR a rating of 2 on the Residue scale in any location) on the 8-week videofluoroscopic swallowing examination, s/he will no longer continue participation in the study. If a patient in either group remains dysphagic at the 8-week visit, s/he will continue participation in the study through the 12-week assessment point. [name] or a UW Voice and Swallowing clinician will conduct the 8 and 12 week assessments.

**Group 1: Compensatory treatments only:** This group will receive standard swallowing intervention, which is identified by the SLP as appropriate to treat the patient's dysphagia and is common clinical practice. This group is not receiving experimental therapy. Their therapy may include: 1) modifying the foods the subject eats or the fluids s/he drinks; 2) changing his/her posture when eating or drinking (for example, by a simple chin tuck) or using a swallowing maneuver while eating or drinking; 3) having him/her eat more slowly or in a quiet environment to make swallowing easier and safer; or 4) performing range of motion or vocal exercises for

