*Muscle Soreness:* Subjects who report muscle soreness during the treatment protocol will be offered breaks throughout treatment sessions if needed.

*Abstaining from strengthening approaches to dysphagia treatment in the acute post-stroke phase of recovery:* There may be unknown risks for subjects randomized to Group 1 who will be abstaining from strengthening approaches for the treatment of dysphagia that might be included as part of standard care. As there is not a clear standard regarding strengthening approaches for dysphagia rehabilitation post-stroke, it is unclear if omission of these approaches will result in adverse effects.

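### Time since stroke can range from the acute admission to 6 months but is neither a stated stratum nor a covariate: a modest precision and conditional-bias issue in arms of 15

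*Combined protocol and SAP*

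**What the plan says.** **Entry window.** The inclusion criteria (Subjects) ask for "2) within 6 months of acute stroke diagnosis; 3) referral for a videofluoroscopic swallowing study" and set no minimum time. Under Recruitment Process in the same section, an emergency physician "will be screening the list of admitted emergency patients daily for those who meet study criteria based on stroke diagnosis"; outpatients are also eligible. Data Safety and Monitoring lists a risk for controls under the label "Abstaining from strengthening approaches to dysphagia treatment in the acute post-stroke phase of recovery", so the plan expects some subjects to be in that phase.

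**Allocation.** Intervention says that eligible participants "will be randomly assigned into one of two groups". No strata, blocks or minimisation are described anywhere.

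**Models.** In Statistical Analyses the Aim 1 model is "adjusted for age, gender, and baseline tongue strength", and the Aim 2 models are fitted "adjusting for age, gender, and baseline outcome". Aim 3 uses age, gender and the pre-study outcome. Outcomes adds treatment compliance as a covariate. Time since stroke appears in no model, subgroup or sensitivity analysis.

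**Expected change without training.** The sample size section assumes a mean gain of 20 hPa in controls and 100 hPa with therapy, with an SD of 100 hPa. It does not relate the control gain to time since stroke.

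**The concern.** The Aim 1 and Aim 2 outcomes are changes over the 8 to 12 weeks after baseline. If patients enrolled soon after stroke improve more without therapy than those enrolled months later, time since stroke predicts the outcome. The design lets it vary widely and leaves it unmodelled. Baseline tongue strength need not stand in for it, because two patients with equally weak tongues can be at different stages of recovery. Compliance is measured after randomisation and says nothing about stage.

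With 15 per arm, chance can give one arm noticeably more early patients, and part of the observed difference would then reflect natural recovery. This matters because the pilot exists to supply figures for sizing a larger trial, so a shifted effect estimate or an SD wider than necessary carries forward.

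**Working it through.** **Inputs from the plan (Sample size calculation, Table 2):** n = 15 per group; SD 100 hPa; alpha 0.05; control gain 20 hPa; planned difference 100 − 20 = 80 hPa; stated power 56%.

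**Inputs that are assumptions:** half of 30 subjects are early; early subjects gain G hPa more than late ones without therapy. The documents give neither figure.

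**1. The plan's own figure.** Two-sided two-sample t-test, noncentral t with 28 df: SE = 100·√(2/15) = 36.5 hPa and noncentrality = 80/36.5 = 2.19, giving 56.2% power. The other rows of Table 2 also reproduce: 75.3%, 35.5% and 18.5% against the stated 75%, 35% and 18%.

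**2. A ceiling for G.** With half the controls early, the control mean is late gain + G/2 = 20. If late controls do not lose strength, G is at most 40 (early +40, late 0). G = 80 would mean early +60 and late −20. In general G cannot exceed 20 divided by the early share, so a larger gap needs fewer early subjects.

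**3. How often the arms differ.** The early count in one arm is hypergeometric (30 subjects, 15 early, 15 drawn).
- Early counts differ by 3 or more: 46.6% of allocations.
- Early counts differ by 5 or more: 14.3% of allocations.

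**4. Shift in the estimate = G × (difference in early counts)/15.**

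| Difference in early counts | G = 20 | G = 40 | G = 40, share of 80 hPa |
|---|---|---|---|
| 3 | 4.0 hPa | 8.0 hPa | 10% |
| 5 | 6.7 hPa | 13.3 hPa | 17% |

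Against the SE of 36.5 hPa, 13.3 hPa is 0.36 SE.

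**5. Overall error rate.** In simulation (100,000 replicates, time since stroke uniform over 0 to 6 months), the unadjusted test rejects a true null in 5.0% of trials at a correlation of 0.3 and in 4.9% at 0.5. Among the 17% of trials with a standardised imbalance above 0.5, the rates are 7.5% and 11.6%, falling to 4.9% and 4.8% after adjustment. These correlations are stronger than G = 40 implies: (40/2)/100 = 0.2.

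**6. Power after adjustment.** Residual SD = √(100² − G²/4). For G = 40 this is √9,600 = 98.0 hPa; with 27 df (time since stroke as the only covariate), power is 57.8%. For G = 20 it is 99.5 hPa and 56.5%. These figures assume that the arms are balanced on early versus late. Without stratification, the mean squared difference in early counts is 4 × 15 × ¼ × 15/29 = 7.76. The squared correlation between arm and early status therefore averages 7.76/225 = 1/29, and the variance of the adjusted estimate rises by about 1/(1 − 1/29) = 1.036. The effective SD at G = 40 is then 98.0 × √1.036 = 99.7 hPa, so power is again about 56%. If time since stroke is not prognostic at all, the loss is 0.1 point by formula and about 1 point in simulation.

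**7. Degrees of freedom** (one change per subject): 30 − 2 (intercept, arm) − 3 (age, gender, baseline) = 25. Adding time since stroke leaves 24, or 23 if compliance is also fitted.

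**The case against.** The strongest objection is that no document relates time since stroke to change in tongue pressure. The 20 hPa control gain is not attributed to natural recovery. The section on dose response says that both acute and chronic patients were still improving at the end of 8 weeks of therapy, without contrasting them. This stands, so the gap can only be an assumption, and with a weak relation the effect is negligible.

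Second, chance imbalance is already in the standard error. A reader might infer that the omission inflates the false-positive rate or favours therapy. It does neither: the overall rate stays at 5%, and an imbalance can as easily hide a benefit.

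Third, the early end of the window may be narrower than the screening suggests, because entry also needs medical stability, decision-making capacity, ability to do the exercises and ability to return to clinic. That is fair, but these conditions set no minimum time.

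Fourth, stroke type, stroke severity and site are also unstratified and unadjusted, and 30 subjects cannot carry many covariates. That is also fair. Time since stroke has a practical claim, because its date is already needed to apply the entry window. The absence of strata is itself inferred from a one-line description of randomisation.

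**Conclusion.** The omission is real and its consequence modest. It is a matter of precision and conditional bias, not of validity. With half of 30 subjects early and a 40 hPa gap, a shift of at least 8 hPa occurs in 47% of allocations and one of at least 13 hPa (17% of the planned difference) in 14%, in either direction; smaller gaps scale these down. The power gain is at most about 2 points. The main reason to adjust is therefore protection against an unlucky allocation.

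Two stronger readings are tempting. One is a larger shift: a gap of 80 hPa would give 80 × 5/15 = 27 hPa for a 5-subject imbalance. With half the subjects early, that gap needs late controls to lose 20 hPa, which nothing in the plan suggests. The other is to carry the argument to Aim 3. Pneumonia and readmissions are counted over up to 9 months (Outcomes) or a 1-year period (Statistical Analyses) before and after the study. They are not 8 to 12 week changes in swallowing, so the recovery argument does not support a change there.

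**What to change.** Pre-specify days from stroke diagnosis to randomisation as a baseline covariate in the Aim 1 and Aim 2 models, on the log scale or as early versus late with the cut fixed in advance. The diagnosis date is already needed for eligibility, so no new data, visits or patients are required. The cost is one degree of freedom of about 25, and up to about 1 point of power if the variable proves not to be prognostic. Fixing it now also avoids a post-hoc decision should an imbalance appear.

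Optionally, stratify the allocations still to be made by the same early/late cut. This changes only the randomisation list and keeps the small precision gain that unstratified adjustment would largely give back. If the list cannot be changed, the covariate alone is enough. No change to the Aim 3 model is proposed on this ground.
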